### 6.2.3 STUDY INTERVENTION

---

[figure not shown]
#### 6.2.3.1 PATIENT MONITORING

Participants will be monitored throughout using **non-invasive hemodynamic monitoring** (Cheetah NICOM monitor). The NICOM monitor has been extensively validated, has FDA approval and is CE marked. Data is collected through 4 ECG-type sensors (size 108 x 20 mm) placed on the front or back of the thorax, as shown in Figure 4. Measurements are not prone to movement artefact. The monitor allows for continuous cardiovascular monitoring (including cardiac output and peripheral resistance), and will allow us to monitor the effects of intramuscular adrenaline on the cardiovascular system.

---

**Figure 4: NICOM Sensor placement**

Respiratory monitoring (respiratory rate, oxygen saturations and peak flow) will be performed at regular intervals (prior to, and 10min, 25min, 65min, 125min, 185min after AAI administration).

#### 6.2.3.2 SELF-ADMINISTRATION OF AAI

Participants will be randomised (see Figure 3) as to the order of AAIs administered. In addition, participants will be randomised separately to receive their Emerade dose on the left or right thigh in a 1:1 ratio (with the Epipen dose given on the opposite side at the appropriate time). Each participant will have a printed randomisation log confirming the order of the AAI administrations and the side used for Emerade injection.

Prior to self-administration of the AAI, the participant will receive a demonstration of AAI administration technique and location using a trainer pen, and be asked to demonstrate this on themselves with a trainer pen, prior to actual administration. Administration will be supervised by a trained clinician.

Following administration, the participant will be asked to remain semi-recumbent on a bed for 3 hours. Participants may drink clear fluids but should avoid food for 2 hours, in order to avoid post-prandial effects on endogenous adrenaline levels.

Any AEs reported by the participant will be recorded on a dedicated Case Report Form.

#### 6.2.3.3 BLOOD SAMPLING AND PROCESSING

4ml blood samples (plasma) will be obtained from the venous cannula at the following timepoints AFTER self-injection: 5, 10, 15, 20, 30, 45, 60, 80, 100, 120 and 180 minutes. A maximum of 2.5ml/kg blood will be withdrawn during each study visit. Oral fluid intake will be encouraged and intake volumes monitored.

Blood samples will be taken into sealed Lithium Heparin tubes and immediately put on ice. They will then be transferred at the earliest opportunity to an on-site sample processing laboratory and centrifuged at 2500g, 4°C for 15 mins, then aliquoted and snap frozen at -80°C. Samples will be batched and then transferred on dry ice to the Department of Clinical Biochemistry at the Royal Brompton Hospital for catecholamine measurement.

## 7 ADVERSE EVENT REPORTING

### 7.1 DEFINITIONS

**Adverse Event (AE):** any untoward medical occurrence in a patient or clinical trial subject administered a medicinal product and which does not necessarily have a causal relationship with this treatment. *An AE can therefore be any unfavourable and unintended sign (including an abnormal laboratory finding), symptom, or disease temporally associated with the use of an investigational medicinal product (IMP), whether or not considered related to the IMP.*

An adverse event will be followed until it resolves or until 30 days after a participant terminates from the study, whichever comes first.

**Adverse Reaction (AR):** all untoward and unintended responses to an IMP related to any dose administered. *All AEs judged by either the reporting investigator or the sponsor as having reasonable causal relationship to a medicinal product qualify as adverse reactions. The expression reasonable causal relationship means to convey in general that there is evidence or argument to suggest a causal relationship.*

**Unexpected Adverse Reaction:** an AR, the nature or severity of which is not consistent with the applicable product information (eg investigator's brochure for an unapproved investigational product or summary of product characteristics (SmPC) for an authorised product). *When the outcome of the adverse reaction is not consistent with the applicable product information this adverse reaction should be considered as unexpected. Side effects documented in the SmPC which occur in a more severe form than anticipated are also considered to be unexpected.*

**Serious Adverse Event (SAE) or Serious Adverse Reaction:** any untoward medical occurrence or effect that at any dose

- **Results in death**
- **Is life-threatening** – refers to an event in which the subject was at risk of death at the time of the event; it does not refer to an event which hypothetically might have caused death if it were more severe
- **Requires hospitalisation, or prolongation of existing inpatients' hospitalisation**
- **Results in persistent or significant disability or incapacity**
- **Is a congenital anomaly or birth defect**

Medical judgement should be exercised in deciding whether an AE/AR is serious in other situations.

Important AE/ARs that are not immediately life-threatening or do not result in death or hospitalisation but may jeopardise the subject or may require intervention to prevent one of the other outcomes listed in the definition above, should also be considered serious.

**Suspected Unexpected Serious Adverse Reaction (SUSAR):** any suspected adverse reaction related to an IMP that is both unexpected and serious.

**Any symptoms requiring treatment for anaphylaxis** (adrenaline, steroids, salbutamol) **will be classified as a SERIOUS ADVERSE REACTION** and must be documented on both the CRF as well as through completion of a SAE form. The investigator should also make a notification to the MHRA through the yellow card scheme (<https://yellowcard.mhra.gov.uk/>).

For the purpose of this study, SARs and SAEs will only be collected where onset is within 24 hours of AAI administration.

### 7.1.1 DOCUMENTATION OF ADVERSE EVENTS

Safety data will be recorded on a specifically designed case report form (CRF). All serious adverse events (SAEs) or reactions (SARs) will be reported on a SAE report form in addition to CRFs. Throughout the study, the investigator will record all adverse events on the appropriate CRF regardless of their severity or relation to study medication or study procedure. The investigator will treat participants experiencing adverse events appropriately and observe them at suitable intervals until their symptoms resolve or their status stabilizes.

SAEs will be reported within 24 hours of the Site Study Team becoming aware of the event. All SUSARs will be reported by the CI to the relevant Competent Authority, Sponsor, REC and other parties, as applicable. For fatal and life-threatening SUSARs, this will be done no later than 7 calendar days after the Sponsor or delegate is first aware of the reaction. Any additional relevant information will be reported within 8 calendar days of the initial report. All other SUSARs will be reported within 15 calendar days. All SAE information must be recorded on an SAE form and emailed to the JRCo ([[contact]](mailto:[contact])).

SARs will also be reported to MHRA through the yellow card system.

### 7.2 GRADING AND ATTRIBUTION OF ADVERSE EVENTS

The study site will grade the severity of adverse events experienced by study participants according to the criteria set forth in the NCI-CTCAE Version 3.0

([http://ctep.cancer.gov/protocolDevelopment/electronic\\_applications/docs/ctcaev3.pdf](http://ctep.cancer.gov/protocolDevelopment/electronic_applications/docs/ctcaev3.pdf)).

This document provides a common language to describe levels of severity, to analyse and interpret data, and to articulate the clinical significance of all adverse events.

Adverse events will be graded on a scale from 1 to 5 according to the following standards in the NCI-CTCAE manual:

Grade 1 = mild adverse event.

Grade 2 = moderate adverse event.

Grade 3 = severe and undesirable adverse event.

Grade 4 = life-threatening or disabling adverse event.

Grade 5 = death.

All adverse events will be recorded and graded whether they are or are not related to disease progression or treatment. The NCI-CTCAE grades will be the primary source for scoring.

The relation, or attribution, of an adverse event to study participation will be determined by the investigator and recorded on CRF and/or SAE reporting form. The assignment of the causality should be made by the investigator responsible for the care of the participant using the definitions in the table below (Table 2). In the case of discrepant views on causality between the investigator and others, all parties will discuss the case. In the event that no agreement is made relating to a SUSAR, the MHRA will be informed of both points of view.

| Relationship          | Description   |
|-----------------------|---|
| Unrelated      | There is no evidence of any causal relationship   |
| Unlikely       | There is little evidence to suggest there is a causal relationship (e.g. the event did not occur within a reasonable time after administration of the trial medication). There is another reasonable explanation for the event (e.g. the participant's clinical condition, other concomitant treatment).            |
| Possible       | There is some evidence to suggest a causal relationship (e.g. because the event occurs within a reasonable time after administration of the trial medication). However, the influence of other factors may have contributed to the event (e.g. the participant's clinical condition, other concomitant treatments). |
| Probable       | There is evidence to suggest a causal relationship and the influence of other factors is unlikely.  |
| Definitely     | There is clear evidence to suggest a causal relationship and other possible contributing factors can be ruled out.  |
| Not assessable | There is insufficient or incomplete evidence to make a clinical judgement of the causal relationship.   |

**Table 2: Assignment of causality for adverse events**

### 7.3 REPORTING PROCEDURES

All adverse events should be reported. Depending on the nature of the event the reporting procedures below should be followed. Any questions concerning adverse event reporting should be directed to the study coordination centre in the first instance. A flowchart is given below to aid in the reporting procedures.

#### 7.3.1 NON SERIOUS AR/AES

[figure not shown]
All such events, whether expected or not, should be recorded in the adverse event section of the relevant case report form and reported to the study CI within one month of the form being due.

### 7.3.2 SERIOUS AR/AES

Fatal or life threatening SAEs and SUSARs should be reported on the day of occurrence. The SAE form asks for nature of event, date of onset, severity, corrective therapies given, outcome and causality (i.e. unrelated, unlikely, possible, probably, definitely). The responsible investigator should sign the causality of the event. Additional information should be sent to the CI within 5 days if the reaction has not resolved at the time of reporting. Any expected SAR will also be reported via the MHRA yellow card system.

**SAEs:** An SAE/SUSAR form should be completed and emailed to the study CI immediately, who will in turn inform the JRCO (email to [[contact]](mailto:[contact])) within 24 hours.

**SUSARs:** All SUSARs will be reported by the CI to the relevant Competent Authority (MHRA) and to the REC and other parties as applicable. For fatal and life-threatening SUSARs, this will be done no later than 7 calendar days after the Sponsor or delegate is first aware of the reaction. Any additional relevant information will be reported within 8 calendar days of the initial report. All other SUSARs will be reported within 15 calendar days.

Contact details for reporting SAEs and SUSARs:

Email: [[contact]](mailto:[contact])

#### 7.4 TRIAL CLOSURE

The expected study duration is ~2 months for any individual participant.

The study will be considered complete following enrolment of the last patient, completion of all study procedures and determination of plasma catecholamine levels in that patient.

No interim analyses are planned.

The study will be placed on hold and, following discussion with the JRCO, may be terminated early if any of the following occur:

- An SAR (whether expected or not) occurring following AAI administration
- Death of a participant during the study period, from any cause

#### 8. DATA MANAGEMENT

Paper records will be maintained at St Mary's Hospital (Imperial College Healthcare NHS Trust) of all participants enrolled in the study. Data will be collected by paper CRF and then transferred to a password-protected electronic record with participants identified by study number. Cardiovascular data from monitoring equipment will be downloaded straight into the electronic record.

Study data will be kept for 10 years following the child's 18th birthday, and then disposed of securely. Local paperwork will be kept as part of the patient notes/CRF as per local policy.

## 9. STATISTICS AND DATA ANALYSIS

### 9.1 SAMPLE SIZE ESTIMATION

This is an exploratory analysis to assess the pharmacokinetics/pharmacodynamics of self-injection of adrenaline in young people with IgE-mediated food allergy. Existing PK/PD studies have not, in general, used a crossover design, but a parallel design with sample size from 5-9 participants per study arm.

In this study, with a cross-over design and a sample size of 12, we expect to detect, with 80% power, a treatment difference of 0.35pg/ml at a two-sided 0.05 significance level (this is based on pilot data (n=55) where the standard deviation of the difference between baseline plasma adrenaline levels on 2 separate occasions in the same individuals was 0.39 pg/ml). In a previous parallel-design study comparing EpiPen 0.15mg to 0.3mg, the latter dose was associated with plasma levels of, on average, >500pg/ml. We therefore expect a sample size of 12 should provide sufficient power to detect any difference in plasma catecholamine levels following AAI administration due to differences in dose or needle length.

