### 3.1 STUDY OUTCOMES MEASURES

#### 3.1.1 PRIMARY STUDY OUTCOME

- Plasma catecholamine profile – determined through  $C_{max}$ ,  $T_{max}$ , AUC – following self-injection of adrenaline (300mcg, 500mcg) on separate occasions.

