### 9.2 SIGNIFICANCE LEVEL AND CONFIDENCE INTERVALS

95% confidence intervals will be reported. Where comparisons are made between sub-groups a 5% significance level will be used.

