### 9.3 ANALYSES

Descriptive tables of numbers by age, gender, baseline variables and adverse events following AAI administration will be produced.

Paired data will be analysed, according to the paired difference between outcomes within the same individual between the different interventions, with all comparisons to data arising from Emerade 300mcg intervention. The planned analyses will therefore be:

- 1) Difference in peak plasma epinephrine ( $C_{max}$ ), time to  $C_{max}$  ( $T_{max}$ ), area under the plasma epinephrine versus time curve (AUC) between Emerade 300mcg and Emerade 500mcg.
- 2) Difference in peak plasma epinephrine ( $C_{max}$ ), time to  $C_{max}$  ( $T_{max}$ ), area under the plasma epinephrine versus time curve (AUC) between Emerade 300mcg (23mm needle) and Epipen 0.3mg (15mm needle).
- 3) Blood pressure, heart rate, stroke volume and change in PEFR versus plasma epinephrine concentrations over time after AAI administration (compared to both baseline and to Emerade 300mcg) will be explored using analysis of variance, analysis of covariance, and linear regression analyses.
- 4) Change in HRQL measures (FAQLQ, FAIM, self-efficacy) 1 month following each study visit, compared to baseline.

Other exploratory analyses:

- 1) Pharmacokinetic parameters of IM adrenaline injection ( $T_{1/2}$ , terminal elimination half-life;  $Cl$ , total body clearance;  $Vdss$ , volume of distribution at steady state) will be calculated from plasma epinephrine concentration versus time plots using Prism.
- 2) For the comparison between Emerade 300mcg (23mm needle) and Epipen 0.3mg (15mm needle), a sub-analysis of the difference in  $C_{max}$ ,  $T_{max}$  and AUC will be undertaken with reference to body weight, BMI and STMD.

Statistical differences will be determined using paired T-test for parametric data, or Wilcoxon signed-rank test for non-parametric data.

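### The 80% power and 0.35 pg/ml in section 9.1 rest on baseline adrenaline variability, so power for post-injection Cmax, Tmax and AUC is not shown

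*Combined protocol and SAP*

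**What the plan says.** Section 9.1 (Sample Size Estimation) opens by labelling the work exploratory: "This is an exploratory analysis to assess the pharmacokinetics/pharmacodynamics of self-injection of adrenaline in young people". It notes that earlier studies used parallel designs with 5 to 9 participants per arm.

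It then makes a formal power statement for its 12 participants: "we expect to detect, with 80% power, a treatment difference of 0.35pg/ml". The test level is two-sided 5%. The basis is pilot data (n=55) in which "the standard deviation of the difference between baseline plasma adrenaline levels on 2 separate occasions in the same individuals was 0.39 pg/ml". Next it cites a parallel-design study of EpiPen 0.15 mg and 0.3 mg, with plasma levels averaging above 500 pg/ml at the higher dose. From these it infers that "a sample size of 12 should provide sufficient power to detect any difference in plasma catecholamine levels following AAI administration", whether the difference is due to dose or to needle length.

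Section 3.1.1 defines the primary outcome as the catecholamine profile (Cmax, Tmax, AUC) "following self-injection of adrenaline (300mcg, 500mcg) on separate occasions". Section 9.3 (Analyses) compares these three parameters as within-person differences, for dose (Emerade 300 mcg against 500 mcg) and for device (Emerade 300 mcg against EpiPen 0.3 mg). The test is specified as: "Statistical differences will be determined using paired T-test for parametric data, or Wilcoxon signed-rank test for non-parametric data".

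**The concern.** The SD in the power statement belongs to a different quantity from the one to be tested. It describes how much resting, endogenous adrenaline varies between two occasions. It contains nothing of the variation in absorption and injection depth that arises once a dose is given, although sections 1.1 and 1.2 present both as central. The crossover removes stable differences between people. It does not make injection-to-injection variation equal to baseline variation.

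The units do not carry over either. Tmax is a time and AUC is concentration multiplied by time, so a figure in pg/ml says nothing about two of the three primary parameters.

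The 500 pg/ml figure does not fill the gap. It is an average with no measure of spread. Even if it were read as a difference between doses, it concerns 0.15 mg and 0.3 mg in a parallel study and still has no paired SD.

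Finally, every test of fixed size has a smallest difference it can reliably detect. Section 9.1 states one and then claims power without limit. A reader who relies on that sentence could take a non-significant contrast, particularly for needle length, as informative when its precision is unknown.

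**Working it through.** **Inputs from section 9.1:** n = 12, difference 0.35 pg/ml, SD of paired difference 0.39 pg/ml, two-sided alpha 0.05, target power 80%.

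**Step 1: reproduce the plan's figure.** Power comes from the noncentral t distribution with noncentrality (difference / SD) × √n = (0.35 / 0.39) × √12 = 3.11.

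- 11 df (paired t-test): 80.8%.
- 10 df (two-sequence crossover): 80.0%.

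The arithmetic reproduces, with 0.39 used as the SD of the difference. The fault lies in the input.

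**Step 2: what 12 pairs give for any SD (paired t-test, 11 df).**

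- Difference detectable with 80% power = 0.889 × SD of the paired difference. Check: 0.889 × 0.39 = 0.347 pg/ml.
- 95% CI half-width = t(0.975, 11) / √12 × SD = 2.201 / 3.464 × SD = 0.635 × SD.

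The 0.35 pg/ml would apply after injection only if the post-injection paired SD were also about 0.39 pg/ml. For scale, 0.35 / 500 = 0.07% of the cited average level. If the paired SD of Cmax were 100, 200 or 400 pg/ml (assumed values), the detectable difference would be 89, 178 or 355 pg/ml.

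**Step 3: illustration on the log scale.** The documents give no CV and no expected ratio, so every CV and ratio here is an assumption. Section 9.3 does not specify a log transformation; it is used here only so that effects can be expressed as ratios. SD of the paired log difference = √(2 ln(1 + CV²)). The ratio 5/3 is 500/300, that is, dose-proportional Cmax. The ratios 1.25 and 2 are illustrative needle-length effects. The detectable ratio is exp(0.889 × SD) and the CI factor is exp(0.635 × SD).

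| Within-person CV | SD of log difference | Power, ratio 5/3 | Power, ratio 1.25 | Power, ratio 2 | Detectable ratio (80% power) | 95% CI: estimate ÷ and × |
|---|---|---|---|---|---|---|
| 20% | 0.280 | >99% | 71% | >99% | 1.28 | 1.20 |
| 30% | 0.415 | 97% | 40% | >99% | 1.45 | 1.30 |
| 40% | 0.545 | 84% | 25% | 98% | 1.62 | 1.41 |
| 50% | 0.668 | 67% | 18% | 90% | 1.81 | 1.53 |
| 60% | 0.784 | 54% | 15% | 80% | 2.01 | 1.65 |
| 80% | 0.995 | 37% | 11% | 60% | 2.42 | 1.88 |

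**Step 4: CV at which power reaches 80%.** Set SD = ln(ratio) / 0.889 and solve for CV.

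- Ratio 5/3: 0.511 / 0.889 = 0.575, so CV ≈ 42%.
- Ratio 1.25: 0.223 / 0.889 = 0.251, so CV ≈ 18%.
- Ratio 2: 0.693 / 0.889 = 0.780, so CV ≈ 60%.

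Power depends strongly on a CV and an effect size that section 9.1 does not supply, and it can differ sharply between the dose and needle-length contrasts that the section covers with one claim.

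**The case against.** The best defence is that little hangs on the sentence. The study calls itself exploratory, compares its size with earlier studies of 5 to 9 per arm, and words its conclusion as an expectation. No analysis in section 9.3 uses 0.35 pg/ml or 80% power. Section 9.2 (Significance level and confidence intervals) promises that "95% confidence intervals will be reported", which would expose poor precision. Nothing in the documents plans to read a non-significant PK contrast as no difference; the PK hypotheses in section 2.3 are directional. For the primary dose contrast, power is at least 84% at CVs up to 40% under dose proportionality. The 1.25 ratio has no source in the documents, and a ratio of 2 gives a much better picture.

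Much of this stands. It limits the consequence, and it is why the illustrations must be read as a range. The multipliers also apply to a paired t-test and not to the Wilcoxon alternative, which may matter for Tmax because it is observed only at the 11 sampling times in section 6.2.3.3.

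None of it rescues the power statement. An exploratory label does not validate a specific 80% figure, and confidence intervals at the end do not supply the missing SD at the start. Relabelling 0.35 pg/ml as a baseline figure would be accurate, but it would leave a number that does not bear on the outcome being tested.

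**Conclusion.** Wrong as written, and it should be fixed. The 80% power for 0.35 pg/ml is computed correctly but describes repeated undosed adrenaline levels. The documents contain no SD, CV or target difference for post-injection Cmax, Tmax or AUC, so power for the primary outcome is not shown, and the unlimited conclusion cannot hold at any fixed sample size.

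This does not show that 12 is too few. What can be stated without further assumptions about variability is relative to the SD of the paired difference: 0.89 times it for the difference detectable with 80% power, and 0.64 times it for the 95% CI half-width. Both assume 12 complete pairs and a paired t-test. The CV thresholds of about 42% (ratio 5/3), 18% (1.25) and 60% (2) also rest on assumed ratios and log-normal data.

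**What to change.** In section 9.1:

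- Delete the statement of 80% power for 0.35 pg/ml and the sentence claiming sufficient power after injection.
- Justify 12 as an exploratory size, citing the earlier studies of 5 to 9 per arm, and feasibility if that was a reason.
- Add: *With 12 complete pairs, the 95% CI half-width is 0.64 times the SD of the paired difference, and the difference detectable with 80% power is 0.89 times that SD (paired t-test).*
- If the sponsor holds a paired SD for post-injection Cmax, insert it and give the resulting difference.
- State that Tmax, AUC and the needle-length contrast are estimated with 95% CIs and no power claim, and that a non-significant result is not evidence of no difference.

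If Cmax is to be analysed on the log scale, say so in section 9.3 (Analyses) as well, and give the detectable ratios by CV from the table above.

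The cost is wording only. Design, enrolment and data collection are unchanged. The one drawback is that the stated sensitivity will look less favourable.
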